4.3 Screen Failures

Screen failures are defined as patients who consent to participate in the clinical study but who do not meet 1 or more criterion required for participation and are not subsequently progressed to treatment in the study. A minimal set of screen failure information is required to ensure transparent reporting of screen failure patients, to meet the Consolidated Standards of Reporting Trials publishing requirements, and to respond to queries from regulatory authorities. Minimal information includes demography, screen failure details, eligibility criteria, and any SAE(s).

Individuals who are screen failures due to out of range laboratory values can be rescreened once. Rescreened individuals retain the same screening number as used for the initial screening.

4.4 Premature Discontinuation

4.4.1 Premature Discontinuation of Investigational Product

Patients should discontinue ATI-450 if any of the following occurs:

- Serious infection
- Invasive fungal infection
- Malignancy (except for non-melanoma skin cancer)
- Hepatitis B virus reactivation

- Demyelinating disease
- Heart failure
- Lupus-like syndrome
- Hypersensitivity reaction
- Gastrointestinal perforation
- WBC count: $<1\times10^3/\mu$ L
- ANC: $<0.5 \times 10^3 / \mu L$
- Lymphocyte count: $<0.3\times10^3/\mu$ L
- Platelet count: $<50\times10^3/\mu$ L
- Hemoglobin: <6.5 g/dL
- AST or ALT:
 - o ≥5×ULN persisting for 2-weeks after study medication interruption or second occurrence of ≥5×ULN
 - \circ ≥3×ULN and total bilirubin ≥2×ULN or international normalized ratio [INR] >1.5
 - ≥3×ULN with appearance of fatigue, nausea, vomiting, right upper quadrant pain or tenderness, fever, rash, and/or eosinophilia (>5%)
- Serum creatinine: >2×ULN persisting for 2-weeks after study medication interruption or second occurrence of >2×ULN
- Confirmed, active infection with the severe acute respiratory syndrome coronavirus 2 (SARS-CoV-2 virus)
- The patient withdraws his/her consent to participate in the study
- The patient develops an illness that would interfere with his/her continued participation in the study
- The patient is noncompliant with study procedures or medication, in the opinion of the investigator
- The patient is confirmed to be pregnant
- The sponsor or regulatory agency requests withdrawal of the patient

- Severe AEs or SAEs
- Any other reason relating to the patient's safety

The investigator will make every effort to ensure that patients who prematurely discontinue ATI-450 complete the end of study assessments.

Patients who discontinue ATI-450 prematurely may be replaced at discretion of the sponsor.

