5.3.2.1 Potential Drug-induced Liver Injury

Hy's Law cases have the following 3 components:

- 1. The drug causes hepatocellular injury, generally shown by a higher incidence of \geq 3-fold elevations above the ULN of ALT or AST than the placebo
- 2. Among study patients showing such aminotransferase elevations, often with aminotransferases much greater than 3×ULN, one or more also shows elevation of serum total bilirubin to >2×ULN or INR >1.5, without initial findings of cholestasis (elevated ALP)
- 3. No other reason can be found to explain the combination of increased aminotransferase and total bilirubin, such as viral hepatitis A, B, or C; evidence for biliary obstruction; acute alcoholic hepatitis (recent drinking and AST >2×ALT are supportive); recent history of severe hypotension or congestive heart failure; other underlying viral disease; pre-existing or acute liver disease; or another drug (including non-prescription products such as herbal supplements) capable of causing the observed injury

During the study, the investigator will remain vigilant for increases in liver biochemistry. The investigator is responsible for determining whether a patient meets potential drug-induced liver injury criteria at any point during the study.

In the event that a patient shows laboratory results of:

- AST or ALT:
 - >5×ULN persisting for 2-weeks after study medication interruption or second occurrence of >5×ULN

- \circ >3×ULN and (total bilirubin >2×ULN or INR >1.5)
- >3×ULN with appearance of fatigue, nausea, vomiting, right upper quadrant pain or tenderness, fever, rash, and/or eosinophilia (>5%)

Please refer to Appendix 1 Possible Hy's Law Liver Chemistry Action and Follow-up Assessments Possible Hy's Law Liver Chemistry Action and Follow-up Assessments for further information.

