16 APPENDICES

16.1 Appendix 1 Possible Hy's Law Liver Chemistry Action and Follow-up Assessments

Suggested Actions and Fe	ollow-up Assessments					
Actions	Follow-Up Assessments					
 Immediately discontinue study medication. Report the event to the sponsor or designee within 24 hours. Complete a SAE data collection tool if the event also met the criteria for an SAE.² Perform liver chemistry follow-up assessments. Monitor the participant until liver chemistry test abnormalities resolve, stabilize, or return to baseline (see MONITORING). Do not restart/re-challenge participant with study treatment unless allowed per-protocol and sponsor approval is granted. If restart/re-challenge is either not allowed per-protocol or not granted, permanently discontinue study treatment. The participant may continue in the study for any protocol-specified follow-up assessments 	 Viral hepatitis serology³ Obtain INR and recheck with each liver chemistry assessment until the transaminase's values show downward trend Obtain blood sample for ATI-450 drug concentration⁴ Serum creatine phosphokinase (CPK) and lactate dehydrogenase (LDH) Fractionate bilirubin if total bilirubin ≥2xULN Obtain complete blood count with differential to assess eosinophilia Record the appearance or worsening of clinical symptoms of liver injury, or hypersensitivity, on the AE eCRF Record use of concomitant medications 					
MONITORING: If ALT ≥3xULN AND bilirubin ≥2xULN or INR >1.5:	(including acetaminophen, herbal remedies, and other over-the-counter medications) on the concomitant medications CRF					
 Repeat liver chemistry tests (ALT, AST, ALP, bilirubin) and perform liver event follow-up assessments within 24 hours. Monitor participant twice weekly until liver chemistry test abnormalities resolve, stabilize, or return to baseline. A specialist or hepatology consultation is recommended. If ALT ≥3xULN AND bilirubin <2xULN and INR ≤1.5: Repeat liver chemistry tests (include ALT, AST, ALP, bilirubin) and perform liver chemistry follow-up assessments within 24 to 72 hours. 	fALT ≥3xULN AND bilirubin ≥ 2xULN or NR >1.5: Anti-nuclear antibody, anti-smooth muscle antibody, Type 1 anti-liver kidney microsomal antibodies, and quantitative total immunoglobulin G (IgG) or gamma globulins. Serum acetaminophen adduct enzyme immunoassay(quantifies potential acetaminophen contribution to liver injury in participants with definite or likely acetaminophen use in the preceding week.					

Page 68 of 71

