•	Monitor participants weekly until liver	
	chemistry abnormalities resolve, stabilize, or	
	return to baseline.	

- 1. Serum bilirubin fractionation should be performed if testing is available. If serum bilirubin fractionation is not immediately available, discontinue study treatment if ALT ≥3xULN and bilirubin ≥2xULN. Additionally, if serum bilirubin fractionation testing is unavailable, record the absence/presence of detectable urinary bilirubin on dipstick which is indicative of direct bilirubin elevations suggesting liver injury.
- 2. All events of ALT ≥3xULN and bilirubin ≥2xULN (>35% direct bilirubin) or ALT ≥3xULN and INR >1.5 may indicate severe liver injury (possible 'Hy's Law') and must be reported as an SAE (excluding studies of hepatic impairment or cirrhosis). The INR measurement is not required, and the stated threshold value will not apply to participants receiving anticoagulants.
- 3. Hepatitis A IgM antibody; HBsAg and hepatitis B Core Antibody (HBcAb); hepatitis C RNA; cytomegalovirus IgM antibody; Epstein-Barr viral capsid antigen IgM antibody (or if unavailable, heterophile antibody or monospot testing); and hepatitis E IgM antibody.
- 4. Drug concentration sample may not be required for participants known to be receiving placebo or non-comparator treatments. Record the date/time of the blood sample draw and the date/time of the last dose of study treatment prior to the blood sample draw on the CRF. If the date or time of the last dose is unclear, provide the participant's best approximation. If the date/time of the last dose cannot be approximated do not obtain a blood sample. Instructions for sample handling and shipping are in the reference manual.

Page 69 of 71

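### Sections 4.4.1, 5.3.2.1 and Appendix 1 state the liver rules with different inequality signs, bracketing and analytes, and two stopping limbs presuppose an interruption that the protocol never specifies

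*Combined protocol and SAP*

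**What the plan says.** **Section 4.4.1 (discontinuation of investigational product)** has three limbs for AST or ALT:
- "≥5×ULN persisting for 2-weeks after study medication interruption or second occurrence of ≥5×ULN";
- ≥3×ULN with total bilirubin ≥2×ULN or INR >1.5, with no brackets grouping bilirubin and INR;
- ≥3×ULN with listed symptoms or eosinophilia.

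The renal limb has the same structure as the first: "Serum creatinine: >2×ULN persisting for 2-weeks after study medication interruption or second occurrence of >2×ULN".

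**Section 5.3.2.1 (potential drug-induced liver injury)** sends the site to Appendix 1 on three AST-or-ALT patterns. The first is ">5×ULN persisting for 2-weeks after study medication interruption or second occurrence of >5×ULN". The other two use >3×ULN, with bilirubin >2×ULN and INR >1.5 joined in brackets, or with the same symptoms.

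**Appendix 1** opens its action list with "Immediately discontinue study medication". It then says "Do not restart/re-challenge participant with study treatment unless allowed per-protocol and sponsor approval is granted". Its monitoring part has two branches, both written for ALT. One is ALT ≥3×ULN with bilirubin ≥2×ULN or INR >1.5. The other begins "If ALT ≥3xULN AND bilirubin <2xULN and INR ≤1.5". Note 2, which lists the events that must be reported as SAEs, also names ALT only.

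Interruptions appear elsewhere only as things to record. Section 6.8 asks for dates of delays and dose reductions. Section 7.1.3 requires a laboratory abnormality that leads to interruption, modification or discontinuation to be recorded as an AE or SAE.

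**The concern.** A stopping rule should give one answer for one set of results. Here the section that stops the drug, the section that refers the patient for liver follow-up and the appendix that describes that follow-up use different conditions. For some results a site can satisfy one and not the next.

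The ≥5×ULN and creatinine limbs raise a separate problem. Their persistence wording starts a two-week clock at an interruption, yet nothing in the protocol starts that interruption, times the retest or says whether dosing may resume. Appendix 1 leaves restart to the protocol, and the protocol is silent.

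Safety is the primary objective, and the multiple-dose part of the healthy-volunteer study dosed for 6.5 days against 12 weeks here. Section 9.4 provides no data monitoring committee. Under Section 7.1.3 an interruption or stop makes AE recording mandatory, so the decision feeds the primary AE counts. It also affects per-protocol membership, which requires 12 weeks of treatment.

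**Working it through.** The plan states no figure to reproduce. The check takes single results, expressed as multiples of ULN (INR as its value), and reads them against each section as written. Values not mentioned are normal, symptoms are absent unless stated, and there has been no earlier interruption.

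| Result | 4.4.1 laboratory stop | Referred by 5.3.2.1 | Appendix 1 text |
|---|---|---|---|
| ALT 3, bilirubin 2 | Yes (≥3, ≥2) | No (needs >3, >2) | Matches first monitoring branch |
| ALT 3.1, bilirubin 2 | Yes | No (needs bilirubin >2) | Matches first monitoring branch |
| ALT 3 with listed symptoms | Yes | No | Matches second monitoring branch |
| ALT 4, bilirubin 2.5 | Yes | Yes | Matches first monitoring branch |
| ALT 4 with listed symptoms | Yes | Yes | Matches second monitoring branch |
| ALT normal, INR 1.6 | Yes if read literally; no if bilirubin and INR are grouped | No | No branch |
| AST 4, bilirubin 2.5, ALT below 3 | Yes | Yes | No branch; outside note 2 |
| First ALT 6, no symptoms | No | No | Not reached |

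**Inequality signs.** Rows 1 to 3 stop under Section 4.4.1 without referral under Section 5.3.2.1. Rows 4 and 5, away from the boundary, agree throughout. The same mismatch applies to a second value of exactly 5×ULN: it meets ≥5 in Section 4.4.1 and fails >5 in Section 5.3.2.1.

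**Bracketing.** Without brackets, 'A and B or C' reads as '(A and B) or C', so INR >1.5 alone would meet Section 4.4.1 (row 6). With the brackets of Section 5.3.2.1 it is 'A and (B or C)', and INR alone does not. Note 2 of Appendix 1 pairs ALT with bilirubin and ALT with INR separately, which agrees with the bracketed form.

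**Analyte.** In row 7 the patient is stopped and referred on AST, then meets neither monitoring branch because both require ALT ≥3×ULN. Note 2 does not reach the event for the same reason.

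**Interruption.** In row 8 no laboratory limb fires on a first value. The persistence half of the ≥5×ULN limb needs an interruption, and no section states the value that starts one. The same is true of creatinine >2×ULN. Nor does the visit schedule supply the two-week value. Table 1 has chemistry on Days 14, 28, 56 and 84, so the gaps are 28 − 14 = 14, 56 − 28 = 28 and 84 − 56 = 28 days. After an interruption at Day 28 or Day 56, a two-week value has to come from an unscheduled sample. Section 5.3.2 asks for repeats of clinically significant values but gives no interval. The timed repeats in Appendix 1 apply to patients already referred there.

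**The case against.** Much can be said for the protocol.

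- **The liver rules are not inoperable as a whole.** Two of the three AST/ALT limbs need no interruption. A second occurrence can be read as a repeat value during continued dosing, needing neither interruption nor restart. The threshold that prompts interruption is arguably implied by the limb itself. This stands, and it confines the gap to the persistence wording; an implied trigger still supplies no retest time or resumption rule.
- **A reader might infer that one asymptomatic ALT of 6×ULN means both continue and stop at once.** The documents do not support that. The text at "If ALT ≥3xULN AND bilirubin <2xULN and INR ≤1.5" sets monitoring frequency and is not an entry criterion. It serves patients already referred for persistent or symptomatic elevations whose bilirubin and INR are below the limits. Nothing tells the site to continue, and the table is headed as suggested actions.
- **A reader might see an SAE conflict** between "Complete a SAE data collection tool if the event also met the criteria for an SAE" and the note saying certain events "must be reported as an SAE (excluding studies of hepatic impairment or cirrhosis". There is none: note 2 is attached to that conditional line and specifies which events qualify.
- **Creatinine does not conflict with Appendix 1**, which has no creatinine rule. It shares only the undefined interruption.
- **The 28-day visit gap does not mean 28 days without a test.** Section 5.3.2 requires review of every laboratory report and repetition of clinically significant values. Section 5.3.2.1 asks for vigilance, and Section 4.4.1 ends with a general patient-safety clause.
- **The sign mismatch needs a value exactly on the limit, and the Appendix 1 repeat panel does include AST.** Both are true and limit the size. An AST-led event could also qualify as an SAE under Section 7.1.2.

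Discretion softens the consequences but does not make the three texts agree.

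**Conclusion.** The point holds as an internal inconsistency that should be fixed. Four defects are on the page: ≥ against >; bracketed against unbracketed bilirubin and INR; AST or ALT against ALT only; and, in the ≥5×ULN and creatinine limbs, an interruption with no trigger, retest time or resumption rule.

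The size is modest in frequency but not negligible in a study this small. The documents give no rate of liver or renal abnormalities, so no expected number of affected patients can be stated. With 10 treated patients, one handled differently changes a patient percentage by 1/10 = 10 points; with fewer the change is larger, and replacement under Section 4.4.1 could alter the denominator.

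The conclusion assumes that Appendix 1 is reached only through Section 5.3.2.1 and that its table is complete as read. The place where note 1 attaches is not visible in the text available, so its scope should be confirmed against the formatted table. No view is taken on which threshold or action is clinically right.

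**What to change.** Reconcile Section 4.4.1, Section 5.3.2.1 and Appendix 1 with its notes so that:
- one set of inequality signs applies throughout;
- the grouping of bilirubin and INR is written the same way in each place;
- one analyte wording is used for the stop, the referral, the monitoring branches and the SAE note;
- the interruption, retest and restart provisions that the ≥5×ULN and creatinine limbs presuppose are stated, and for the liver limb are consistent with the restart line in Appendix 1.

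The sponsor chooses every threshold and action. The cost is amendment wording and site retraining; no extra patients are needed.

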4.4.2 Premature Discontinuation from the Study

Participation in the study is strictly voluntary. A patient has the right to withdraw from the study at any time for any reason, without any reprisal.

The investigator has the right to terminate participation of a patient for any of the following reasons:

- Difficulties in obtaining blood samples
- Violation of the protocol
- Any other reason relating to integrity of the study data

If a patient is withdrawn from the study, the study monitor/sponsor will be informed immediately. If there is a medical reason for withdrawal, the patient will remain under the supervision of the investigator until satisfactory health has returned.

If the patient withdraws consent for disclosure of further information, the sponsor may retain and continue to use any collected data before such a withdrawal of consent. If a patient withdraws from the study, he/she may request destruction of any samples taken and not tested, and the investigator must document this in the site study records.

Although a patient is not obliged to give his/her reason(s) for withdrawing prematurely from a study, the investigator should make a reasonable effort to ascertain the reason(s), while fully respecting the patient's rights.

At the time of premature study discontinuation, the investigator should make every effort to ensure the patient completes the assessments indicated at the end of study (Day 84) and safety follow-up visit (Day 7); see Table 1.

Patients who prematurely discontinue from the study cannot subsequently rejoin the study. For details on the discontinuation of study sites or the study as a whole, see Section 14.

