3 STUDY PLAN

3.1 Overall Study Design and Plan

The study visit schedule and planned assessments at each visit are detailed in Table 1.

This is a Phase 2a, open-label, single-arm study to investigate the safety, tolerability, efficacy, PK, and PD of ATI-450 to maintain remission in patients with CAPS previously managed with anti-IL-1 therapy. Up to 10 patients are planned to be enrolled in the study. The study will consist of an up to 8-week screening period, a 12-week treatment period, and a 4-week safety follow-up period. The total duration of the study for patients remaining in the study until their final safety follow-up assessment will be up to 24 weeks.

The investigator will obtain signed informed consent from the patient before any study procedures are performed. For further details regarding the informed consent process, see Section 9.3. During the screening visit each patient will be required to have all assessments performed as outlined in the Schedule of Assessments (Table 1).

Patients whose eligibility is confirmed at baseline will begin dosing ATI-450 tablets (50 mg BID). Such patients will be in protocol-defined remission due to prior treatment with an anti-IL-1 biologic. Dosing will begin on the day that the next dose of their anti-IL-1 therapy is scheduled at which time anti-IL-1 therapy will be discontinued.

The first dose of ATI-450 (50 mg BID) will be taken at the following times (based on anti-IL-1 therapy):

- Anakinra: 24 hours (+/- 1 hour) after last administration or at approximate time of regular anakinra dose.
- Canakinumab: 8 weeks (+/- 1 week) after last administration.
- Rilonacept: 1 week (+/- 1 day) after last administration.

ATI-450 will be administered orally for 12-weeks. Patients will attend clinic visits on Days 14, 28, 56, and 84 (+/-1 day) for safety, efficacy, PK and PD assessments. Patients will begin recording disease symptoms in their daily diary card 7 days prior to beginning administration of ATI-450, or immediately starting at the screening visit if the Day 1 visit is scheduled to occur less than 7 days after the screening visit. Patients will continue to complete their diary until completion of the safety follow up Day 7 visit.

At the end of 12-weeks, Day 84 (+/- 1 day), patients will stop ATI-450 and conduct end of study assessments. Patients will complete safety follow-up visits on site 7 Days (+4 days) after the last dose of ATI-450 and via a phone call 30 Days (+/-3 days) after the last dose.

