5.1.5 COVID-19 Monitoring

At Baseline Visit 2, all patients entering the treatment phase of the study must have a nasopharyngeal (preferred) or oropharyngeal swab collected prior to the first dose of ATI-450 to test for the presence of the SARS-CoV-2 virus. The sample will be sent to the study's central lab for analysis by reverse transcription polymerase chain reaction (RT-PCR) with results reported as either 'Detected' or 'Not detected' for SARS-CoV-2 viral particles. If central laboratory testing cannot be performed at the time of Baseline Visit 2 (i.e., lab supplies are not yet available) and the study site is able to perform equivalent testing locally, they may choose to do so, as long as the test results are available in the patient's research chart for sponsor review. Patients should not initiate ATI-450 in the absence of central laboratory or locally equivalent testing being performed.

Patients are allowed to dose with ATI-450 in the interval between sample collection at Baseline Visit 2 and result reporting as long as there is no clinical suspicion of COVID-19 infection or recent exposure of the patient to an individual with a confirmed, active infection.

If the patient's results are positive for SARS-CoV-2 following sample collection at Visit 2, the patient will need to be notified immediately upon receipt of the results and treatment with ATI-450 will be permanently discontinued. The patient should be advised to begin self-isolation and self-monitoring procedures according to any applicable local, state, and/or federal health recommendations. Referral to an appropriate health care provider for management of the patient's COVID-19 diagnosis should also be made. The patient should be seen for the safety follow-up Visit 7 (see Table 1) only at such time that the investigator assesses the risk for incidental transmission from viral shedding to be minimized. The patient's COVID-19 diagnosis will be reported as medical history unless the patient's clinical course progresses such that criterion for SAE reporting is met (See Section 7.1.2), in which case, all applicable safety reporting procedures will be followed by the site.

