7.3 Documenting and Reporting Adverse Events

Reporting of SAEs will begin when the patient has provided informed consent and will continue up to the end of study visit or 30 days after the last ATI-450administration whichever is later. Reporting of AEs will begin when the patient receives the first dose of ATI-450 and will continue up to the end of study visit or 30 days after the last study drug administration, whichever is later. Any clinical AE that occurs between the time of consent and dosing Day 1 will be recorded as medical history.

Occurrence of AEs may be volunteered spontaneously by the patient; discovered as a result of general, nonleading verbal questioning by the study staff; or determined by physical examination or other safety assessments. All AEs will be monitored and recorded in the CRF throughout the entire study.

For all AEs, the investigator must pursue and obtain adequate information (a description of the event, severity, time of occurrence [including whether the AE onset was before, during, or after the study medication administration if the AE started on a dosing day], duration, and any action [e.g., treatment/follow-up tests]). The outcome of the event should be provided along with the investigator's assessment of the relationship to the study medication. The investigator must also assess whether the event meets the criteria for classification as an SAE.

It is the investigator's responsibility to review all documentation (e.g., hospital notes, laboratory reports, and diagnostic reports) related to an AE. Wherever possible, the investigator's diagnosis, not the individual signs and symptoms, will be documented as the AE.

Investigators are not obligated to actively seek AEs or SAEs after the patient's conclusion of study participation. However, if the investigator learns of any SAE, including death, at any time after a patient has been discharged from the study, and he/she considers the event to be reasonably related to the study medication or study participation, the investigator must promptly notify the sponsor.

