8.4.2 Safety Analyses

The Safety population will be used for the analysis of safety data (AEs, exposure to study medication, clinical laboratory, vital signs, and ECG).

AEs will be coded with the MedDRA. TEAEs are defined as AEs with an onset date on or after the date of first administration of study medication and before the date of last administration of study medication + 30 days. TEAEs will be presented by system organ class and preferred term in frequency tables. Patients with multiple AEs will be counted only once within each preferred term and system organ class. Key patient information for patients with an AE with an outcome of death, patients with SAEs, and patients with an AE leading to discontinuation of study medication will be listed.

Laboratory data (hematology, serum chemistry, coagulation, lipids, and urinalysis) will be converted to Système International units for reporting and processing purposes. Absolute values and changes from baseline will be presented descriptively. Laboratory data outside study-specific reference ranges will be listed.

Vital signs and ECG parameters will be presented descriptively.

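### For patients who leave the study early, the last named contact is the Day 7 visit, but AE/SAE reporting and TEAE counting run to about 30 days after the last dose

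*Combined protocol and SAP*

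**What the plan says.** **Windows.** Section 7.3 starts AE reporting at the first dose and says that it "will continue up to the end of study visit or 30 days after the last study drug administration, whichever is later". SAE reporting starts at consent and has the same end point. Section 8.4.2 counts an AE as treatment-emergent if it starts on or after the first dose and "before the date of last administration of study medication + 30 days". Neither section makes an exception for patients who stop early.

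**Contacts for completers.** Section 3.1 follows the planned stop at 12 weeks with "safety follow-up visits on site 7 Days (+4 days) after the last dose of ATI-450" and then a contact "via a phone call 30 Days (+/-3 days) after the last dose". Table 1 lists only adverse events and medications for that call (Visit 8).

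**Contacts for early stoppers.**
- Section 4.4.1 (drug stopped): the investigator should make sure that "patients who prematurely discontinue ATI-450 complete the end of study assessments". Table 1 attaches the end-of-study label to Visit 6.
- Section 4.4.2 (study left): the investigator should "ensure the patient completes the assessments indicated at the end of study (Day 84) and safety follow-up visit (Day 7".
- Section 5.1.5 (positive SARS-CoV-2 test at baseline): "The patient should be seen for the safety follow-up Visit 7 (see Table 1) only at such time" as the transmission risk is judged to be minimized. Visit 8 is not mentioned.
- Section 5.3.3 (pregnancy): the patient is withdrawn once the end-of-study assessments are done. Visits 7 and 8 are not mentioned.

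**After participation ends.** Section 7.3 adds: "Investigators are not obligated to actively seek AEs or SAEs after the patient's conclusion of study participation".

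**The concern.** The period over which events count is the same for every dosed patient, but the named contacts at which someone would ask about events are not. Completers have a call designed to close the 30-day window. Section 4.4.2 names one of the two follow-up contacts and omits the other, which invites sites to stop at Day 7. Section 4.4.1 leaves each site to decide whether Visits 7 and 8 still apply once the drug has been stopped.

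Safety and tolerability are the primary objective, and the synopsis analyses safety in all dosed patients. An early leaver therefore stays in the denominator for the full window while being asked about only part of it. The direction of any bias is towards too few TEAEs. Anti-IL-1 therapy normally resumes after the Day 7 assessments, so the days without contact also cover the switch back.

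**Working it through.** The plan has no figure of its own to reproduce here: the sample size rests on feasibility (Section 8.3) and no dropout rate is stated. The check is window arithmetic.

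**Inputs**
- Window: 30 days after the last dose (Sections 7.3 and 8.4.2).
- Day 7 visit: Day 7 to 11 after the last dose (Section 3.1).
- Day 30 call: Day 27 to 33 after the last dose (Section 3.1).
- End-of-study assessments in an early stopper: timing not stated; assumed 0 to 1 day after the last dose.
- Early-stop rate: not stated; assumed 1 to 3 of 10 patients.

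**Formula.** Days without scheduled contact = max(0, 30 − day of last named contact). Share = those days / 30.

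| Last named contact | Days without contact | Share of 30 days |
|---|---|---|
| Day 7 visit, on Day 7 | 30 − 7 = 23 | 76.7% |
| Day 7 visit, on Day 11 | 30 − 11 = 19 | 63.3% |
| End-of-study assessments only, Day 0 to 1 | 30 to 29 | 100% to 96.7% |
| Visit 8 call, Day 27 to 33 | 3 to 0 | 10% to 0% |

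The first two rows apply to Section 4.4.2. The third applies to Section 4.4.1 only if a site reads its silence as meaning that no further visit is due.

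**Across the trial.** With *k* early leavers among 10 dosed patients, 19*k* to 23*k* of 10 × 30 = 300 post-dose patient-days have no scheduled contact:
- *k* = 1: 19 to 23 days (6.3% to 7.7%)
- *k* = 2: 38 to 46 days (12.7% to 15.3%)
- *k* = 3: 57 to 69 days (19.0% to 23.0%)

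**Test case: a new, non-serious AE starting 20 days after the last dose.** It falls inside the TEAE window.
- A completer is asked about it at Visit 8.
- A study leaver was last due to be seen on Day 7 to 11.
- The 30-day duty in Section 7.3 sets a reporting period but supplies no contact.
- Section 7.5 follows events that are already known.
- Supervision under Section 4.4.2 covers withdrawals for a medical reason and ends on recovery, which may come before Day 30.
- Post-study reporting under Section 7.3 covers only SAEs that reach the investigator and are judged reasonably related.

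None of these provisions schedules a question that would find the event.

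**The case against.** The strongest reply is that an unnamed contact is not an unobserved window. Much of that reply stands, and it rules out several stronger readings.

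- **A reader might infer that most of the window goes unobserved.** The documents do not support this. The 30-day duty in Section 7.3 still applies to early stoppers. Medical withdrawals stay under supervision, known events are followed to resolution or stabilization, clinically significant laboratory values are repeated (Section 5.3.2), and possible Hy's Law cases are monitored weekly or twice weekly (Appendix 1). Patients with a recognized safety problem will often remain in contact.
- **A reader might infer that patients who only stop the drug are excused from Visits 7 and 8.** Section 4.4.1 is silent and waives nothing. The follow-up visits are timed from the last dose, and Appendix 1 allows a patient permanently off drug to stay for follow-up. The release from actively seeking events begins when study participation ends, which stopping the drug does not by itself cause.
- **A reader might infer that SARS-CoV-2-positive patients get Visit 7 and nothing else.** The restriction in Section 5.1.5 concerns when Visit 7 takes place, not which visits take place. Visit 7 may then fall later than Day 11.
- **A reader might infer that every missed event moves a TEAE percentage by 10 points.** Patients count once per preferred term and system organ class, so 1/10 applies only to a term not already counted in that patient. Section 4.4.1 allows replacement, so more than 10 may be dosed and the step would be smaller.
- **A reader might infer that a call on Day 27 is a defect for completers.** A tolerance of 3 days either side of Day 30 is ordinary scheduling, and the reporting duty still runs to 30 days.

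It can also be said that late events tell little about the drug. Section 1.1.3 gives a half-life of about 9 to 11 hours, so Day 7 (168 hours) is about 15 to 19 half-lives after the last dose, and resumed anti-IL-1 therapy complicates attribution. That bears on interpretation. It does not explain why the plan counts events to 30 days in all patients but names the closing contact only for some.

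**Conclusion.** The mismatch is real and worth an amendment. For patients who leave the study, 19 to 23 of the 30 post-dose days (63-77%) have no scheduled contact, against 0 to 3 days with the Visit 8 call. New AEs starting in that period depend on passive reporting or on supervision of problems already known, so ascertainment of the primary safety endpoint is shorter than in completers. For patients who stop only the drug, the defect is ambiguity: the text does not say whether Visits 7 and 8 apply.

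The result assumes that sites follow Section 4.4.2 literally and time the Day 7 visit from the last dose. The effect on the trial's safety tables cannot be sized, because neither an early-stop rate nor an event rate is given. The patient-day range of 6.3% to 23.0% rests on the assumed 1 to 3 early leavers in 10. The documents do not support saying that events in this period would go wholly undetected.

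**What to change.** Reconcile Sections 4.4.1 and 4.4.2 with Sections 7.3 and 8.4.2. State that the Day 7 visit and the Day 30 call, both timed from the actual last dose, apply to every dosed patient who stops early and has not refused further contact. Add the same clarification to Section 5.1.5 (Visit 8 follows a Visit 7 that may be delayed) and to Section 5.3.3. The ±3-day window for the call can stay.

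The cost is one phone call per early stopper, of a kind already planned for completers, and a few words in an amendment. After the change, 0 to 3 of the 30 days would lack scheduled contact, as for completers.
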